2 PROTOCOL SUMMARY

Title

A phase 1 clinical trial to evaluate the safety and immunogenicity of HIV-1 vaccines based on chimpanzee serotypes of adenovirus expressing clade C gp140 and a CH505TF gp120 protein boost in healthy, HIV- uninfected adult participants.

Primary objective

To evaluate the safety and tolerability of AdC6-HIVgp140 and AdC7-HIVgp140 at doses of 1×10^{10} virus particles (vp) and 5×10^{10} vp, alone and in combination with CH505TF gp120 adjuvanted with GLA-SE in HIV- uninfected adults.

Study products and routes of administration

- **AdC6-HIVgp140:** a chimpanzee-derived replication-defective adenovirus (Ad) vector expressing codon optimized gp140 of clade C isolate Du422 administered at a dose of 1×10^{10} vp or 5×10^{10} vp. The vaccine dose will be divided equally into two separate 1mL intramuscular (IM) injections, administered into the deltoid of the non-dominant arm unless medically contraindicated.
- **AdC7-HIVgp140:** a chimpanzee-derived replication-defective Ad vector expressing codon optimized gp140 of clade C isolate Du172 administered at a dose of 1×10^{10} vp or 5×10^{10} vp. The vaccine dose will be divided equally into two separate 1mL IM injections administered into the deltoid of the non-dominant arm unless medically contraindicated.
- **CH505TF gp120:** CH505 transmitted/founder gp120 mixed with GLA-SE [the immunological adjuvant Glucopyranosyl Lipid A (GLA) in an oil-in-water stable emulsion (SE)], administered at a dose of 400 mcg with 10 mcg GLA-SE as a 1 mL injection in the thigh unless medically contraindicated.
- Placebo control for AdC6 -HIVgp140 and AdC7-HIVgp140 vaccine: Sodium Chloride for Injection, 0.9%, administered as two separate 1 mL IM injections into the deltoid of the non-dominant arm unless medically contraindicated.
- Placebo control for CH505TF gp120: Sodium Chloride for Injection, 0.9% administered as a 1 mL IM injection in the thigh unless medically contraindicated.

Participants

34 healthy, HIV– uninfected volunteers aged 18 through 50 years, inclusive; 30 vaccinees, 4 placebo recipients.

Schema

Table 2-1 Schema

Study arm	N	AdC dose (vp)	M0	M3	M6
Part A: Low Dose					
Group 1	5	1x 10 ¹⁰	AdC6-HIVgp140	-	-
Group 2	5	1x 10 ¹⁰	AdC7-HIVgp140	-	-
Group 3	2	0	Placebo	-	-
Part B: High Dose					
Group 4	10	5 x 10 ¹⁰	AdC6-HIVgp140	AdC7-HIVgp140	400 mcg CH505TF gp120/GLA-SE
Group 5	10	5 x 10 ¹⁰	AdC7-HIVgp140	AdC6-HIVgp140	400 mcg CH505TF gp120/GLA-SE
Group 6	2	0	Placebo	Placebo	Placebo

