8.1 Immunogenicity analysis

8.1.1 General approach

For the statistical analysis of immunogenicity endpoints, data from enrolled participants will be used according to the initial randomization assignment regardless of how many injections they received. Additional analyses may be performed, limited to participants who received all scheduled injections per protocol. Assay results that are unreliable are excluded; results from specimens collected outside of the visit window, from HIV-infected participants post-infection or from participants with study product administration errors due to wrong dose administered, may be excluded. Since the exact date of HIV infection is unknown, any assay data from blood draws 4 weeks prior to an infected participant's last seronegative sample and thereafter may be excluded. If an HIV-infected participant does not have a seronegative sample post-enrollment, then all data from that participant may be excluded from the analysis.

Discrete categorical assay endpoints (eg, response rates) will be analyzed by tabulating the frequency of positive response for each assay by antigen and treatment arm at each timepoint for which an assessment is performed. Crude response rates and difference between treatment arms will be presented with their corresponding 95% confidence interval estimates calculated using the score test method [1].

For quantitative assay data, graphical and tabular summaries of the distributions by antigen, treatment arm, and timepoint will be made. For all primary and secondary immunogenicity endpoints, box plots and plots of estimated reverse cumulative distribution curves will be used for graphical display of all study arms. Typically, the results will be shown for each vaccine arm and for the set of control arms pooled into one group.

Mean or median (if normality assumption severely violated) assay readouts will be compared between arms and bootstrap confidence intervals will be estimated.

More sophisticated analyses employing repeated measures methodology (for example, linear mixed models or marginal mean models fit by generalized estimating equations) may be utilized to incorporate immune responses over several timepoints and to test for differences over time. However, inference from such analyses would be limited by the small sample size of this study. All statistical tests will be 2-sided and will be considered statistically significant if $p \leq 0.05$.

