
8.1.3 Primary analyses of neutralization magnitude-breadth curves

The area-under-the-magnitude-breadth curve (AUC-MB) to a global panel of viral isolates [4] will be computed for each participant with evaluable neutralization data, as described in [5]. AUC-MB to a vaccine-matched panel may also be computed when the panel consists of at least 3 isolates. Tier 1A viral isolates will not be included in AUC-MB analyses. Dunnett’s procedure will be applied with 2-sided alpha = 0.05 to determine which of the [n] vaccine groups have a significantly higher mean AUC-MB than that of the pooled placebo groups, as described in [2] (see their formula (1.1)). This procedure will be applied to construct 95% Cis about the [n] differences in mean AUC-MB for each vaccine regimen versus the pooled placebo

groups (vaccine – placebo), which simultaneously have at least 95% coverage probability.

8.1.4 Analysis of CD4+ and CD8+ T-cell responses as measured by the ICS assay

The analysis of CD4+ and CD8+ T-cell response rates as measured by the ICS assay will be evaluated and compared as described under the general approach. For each T-cell subset, the positivity call for each peptide pool will include a multiple comparison adjustment for the number of peptide pools used in the assay. In general, the Mixture Models for Single-cell Assays (MIMOSA) statistical framework [6] and/or the Fisher's exact test-based positivity criteria will be used. Details of the positivity criteria will be discussed in Section 9. The magnitude of marginal response will be analyzed as described for quantitative data in the general approach section. For each T-cell subset, graphs will be used to display the background-subtracted magnitudes for each participant by protein, treatment arm and timepoint. When 3 or more cytokines are being measured by the ICS assay, the polyfunctionality of ICS responses may also be analyzed as an exploratory endpoint. Besides descriptive plots of the magnitude of polyfunctional responses, the COMPASS (Combinatorial Polyfunctionality analysis of Antigen-Specific T-cell Subsets) statistical framework [7] may also be used to perform joint modelling of multiple T-cell subsets of different cytokine combinations. For example, the functionality score (FS) and the polyfunctionality score (PFS) may be used to summarize the multi-parameter ICS responses.

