8.1.5 Analysis of multiplexed immunoassay data

When a small panel of analytes (eg, ≤ 5) is being assessed in a multiplexed immunoassay, the analysis of response rates and response magnitudes will be evaluated and compared as described under the general approach. Details for calculating a positive response and response magnitude will be provided in Section 9. When a larger panel is being assessed, two approaches may be considered to evaluate the magnitude and breadth of these responses. First, Magnitude–Breadth (M-B) curves maybe employed to display individual- and group-level response breadth as a function of magnitude. Response breadth is defined as the number of antigens, peptides, and/or isolates with associated magnitudes above the assay-specific positivity threshold. Two choices are to compare the M-B curves among vaccine arms, as follows: a non-parametric Wilcoxon rank sum test on the subject-specific AUC-MB or a Kolmogorov-Smirnov type test on the 2 group-average M-B curves. Simulations can be used to obtain 2-sided p-values for the latter test. Second, a weighted-average score-like variable may be constructed to account for the correlations between analytes as an integrate magnitude of responses to multiple analytes. Similar group comparison methods described in the first approach may be adopted. Details of either approach will be described in Section 9.

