9.2 Intracellular Cytokine Staining

Flow cytometry will be used to examine vaccine related HIV-1-specific CD4+ and CD8 responses using a validated ICS assay. A 17-color panel (experiment Assay ID 109; analysis plan 042) was used [8, 9]. The immunogenicity of this regimen will be assessed by intracellular cytokine staining (ICS) at CHIL for all available samples from participants from:

- Part A (n=11), visit 4 (1 month (M) post vaccination)
- Part B (n=20): visits 4 (M1, post first vaccination), 7 (M4, 1 month post the second vaccination) and 9 (M6.5, two weeks post the final vaccination)

Based on results from the above timepoints, others may be assessed, these include:

- Part A (n=11), visit 5 (M6)
- Part B (n=20): visit 10 (M12)

Several criteria will be used to determine if data from an assay are acceptable and can be statistically analyzed. The blood draw date must have been within the allowable visit window as determined by the protocol and assay results deemed unreliable for analysis by the lab will be excluded from the analysis. Post-infection samples from HIV-infected participants will be excluded. Participants with study administration error due to wrong dose administered will also be excluded. After sample thawing and overnight incubation, the viability of the PBMC must have been 66% or greater for testing to have proceeded. If it was not, a new specimen for that participant at that timepoint will be thawed for testing. If the PBMC viability of the second thawed aliquot is below this threshold, the ICS assay will be not performed, and no data will be reported to the statistical center for the participant and timepoint. For the negative control acceptance criteria, if the average cytokine response for the negative control wells is above 0.1% for either the CD4+ or CD8+ T cells, the sample will be retested. If the retested results are above 0.1%, the data will be excluded from analysis; otherwise, the retest data will be used.

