9.2.1 Lists of Tables

- Response rate table by lab, T-cell subset, cytokine, peptide pool, visit, visit month, and treatment arm for cells expressing a given cytokine using Fisher's exact test criteria.
- Summary statistics of background-adjusted marginal cytokine response magnitude (i.e., min, mean, median, max) among all participants (positive and negative responders) for T-cell subset, cytokine, peptide pool, visit, and treatment arm.
- Summary statistics of background-adjusted marginal cytokine response magnitude (i.e., min, mean, median, max) among responders for T-cell subset, cytokine, peptide pool, visit, and treatment arm.
- Response rate and/or response magnitude comparison of treatment arms.
 - a. Treatment 1 vs. Treatment 4 at 4 weeks after 1st vaccination
 - b. Treatment 2 vs. Treatment 5 at 4 weeks after 1st vaccination
 - c. Treatment 4 vs. Treatment 5 at 4 weeks after 1st vaccination, 4 weeks after 2nd vaccination, 2 weeks after 3rd vaccination, and 6 months after 3rd vaccination

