9.3 Neutralizing Antibody

Assays will be performed on cryopreserved serum samples obtained 4 weeks after the 1st vaccination (M1) for Part A. For Part B, serum samples will be obtained 4 weeks after the 1st vaccination (M1), 4 weeks after the 2nd accination (M4) and 2 weeks after the 3rd vaccination (M6.5). Assays will also be performed on baseline samples (M0) for Part A and Part B.

Neutralizing antibodies against tier 1 and tier 2 strains of HIV-1 will be measured in TZM-bl cells as a function of a reduction in Tat-induced luciferase reporter gene expression after a single round of infection with molecularly cloned, Env-pseudotyped viruses [10]. TZM-bl (also called JC57BL-13) is a HeLa cell clone that was engineered to express CD4 and CCR5 [11] and to contain integrated reporter genes for firefly luciferase and *E. coli* β -galactosidase under control of an HIV-1 long terminal repeat (LTR) [12]. The cells are highly permissive to infection by most strains of HIV, including primary HIV-1 isolates and molecularly cloned Env-pseudotyped viruses. DEAE-dextran (Diethylaminoethyl-Dextran) is used in the medium during neutralization assays to enhance infectivity. Expression of the reporter genes is induced in trans by viral Tat protein soon after infection. Luciferase activity is quantified by luminescence and is directly proportional to the number of infectious virus particles present in the initial inoculum. The assay is performed in 96-well culture plates for high throughput capacity. Use of a clonal cell population provides enhanced precision and uniformity. The assay has been formally optimized and validated for single-round infection with either uncloned or molecularly cloned Env-pseudotyped viruses produced by transfection in 293T cells [13].

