All designated serum samples will be assayed against Tier 1 and Tier 2 strains of virus by starting with a 1:10 dilution of serum to obtain a neutralizing antibody titer. The starting dilution of serum can be adjusted by the primary investigator to ensure obtainment of a neutralizing antibody titer. Titers will be defined as the serum dilution that reduces RLUs by 50% relative to the RLUs in virus control wells after subtraction of background. Each plate will contain 8 wells of cell controls (cells only) and 8 wells of virus controls (cell + virus only). A broadly neutralizing antibody PGDM1400 will serve as a positive control and will be tested on at least one plate in a series. One series of plates constitutes all plates set-up in a single session by a single technician. Mandatory assays with visit 4 and 104 samples (1 month post 1st vaccination) and visit 107 and 109 (1 month post 2nd and 2 weeks post 3rd vaccination respectively) will measure neutralization

titors in TZM-bl cells against the Env-pseudotyped vaccine strains (Du422.1, Du172.17 and CH0505TF) and a virus that exhibits a tier 1A neutralization phenotype (MW965.26). Additional neutralization assays may also be performed with samples against a clade C panel of tier 2 Env-pseudotyped viruses (ZM233M, Ce703010010, 2759058, ZM215F, So431, Ce704810053, 3728, 2969249, B005582, CAP382, Ce2103, and Ko243) and/ or against viruses from a global panel of heterologous tier 2 Env-pseudotyped viruses (246F3, Ce1176, CNE55, X1632, Ce0217, BJOX2000, 25710, TRO11, CH119, X2278, CNE8 and 398F1) [14] Additional assays may be performed in TZM-bl cells to measure neutralization titers against other tier 1 and tier 2 viruses not listed above.

A response is considered positive if the neutralization titer is 10 or above, the starting dilution, which is the limit of detection of the assay. Magnitude of response will be measured by the natural log of the ID50 and ID80 titer.

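### SAP 8.1.1 asks for bootstrap intervals for between-arm means without naming type or level; at 5 to 10 per arm the usual types would cover about 88–92%, not 95%

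*SAP*

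**What the plan says.** Section 8.1.1 of the SAP sets the general rule for magnitude data: "Mean or median (if normality assumption severely violated) assay readouts will be compared between arms and bootstrap confidence intervals will be estimated". The only 95% level in that section belongs to the score intervals for response rates. The two-sided 0.05 rule there belongs to tests. A 95% level for the bootstrap intervals is the natural reading, but it is not stated. Sections 9.1 to 9.4 name no bootstrap type or level.

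The trial has "30 vaccinees, 4 placebo recipients". The schema in Section 2 gives 5 in each of Groups 1 and 2, 10 in each of Groups 4 and 5, and 2 in each placebo group.

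The rule reaches the assays as follows:

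- **ICS.** Section 8.1.4 refers to it directly: "The magnitude of marginal response will be analyzed as described for quantitative data in the general approach section". Section 9.2.1 then lists dose contrasts such as "a. Treatment 1 vs. Treatment 4 at 4 weeks after 1st vaccination", and Treatment 4 against 5.
- **Binding antibody.** For small panels, Section 8.1.5 says "the analysis of response rates and response magnitudes will be evaluated and compared as described under the general approach". The per-antigen net MFI and AUC comparisons in Section 9.4.1 have no other stated interval method, so their route to 8.1.1 is inferred.
- **Neutralization.** Section 9.3.1 lists the dose and sequence contrasts and also Treatment 1 against 2, but its wording allows response rates alone to be compared. On scale, Section 9.3 says: "Magnitude of response will be measured by the natural log of the ID50 and ID80 titer".

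**The concern.** Bootstrap confidence interval is a family name. The members most often used (percentile, basic, BCa) rely on large-sample behaviour and are too short for a difference in means when arms have 5 or 10 observations. The intervals most at issue are the dose contrasts (Treatments 1 v 4 and 2 v 5) and the sequence contrast (4 v 5), which serve secondary objectives 1 to 3.

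If one of those types is used, the report will overstate the precision of dose and sequence differences, and intervals labelled 95% will exclude zero too often. The small-sample caution in Section 8.1.1 is attached to the repeated-measures models, not to these intervals. Leaving the type open also leaves the choice to be made after the data are unblinded.

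**Working it through.** The documents state no coverage figure for these intervals, so there is none to reproduce.

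**Inputs**

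- Arm sizes from the Section 2 schema: 5, 5, 10, 10.
- Contrasts from 9.2.1, 9.3.1 and 9.4.1: 5 v 10 (1 v 4, 2 v 5), 10 v 10 (4 v 5), 5 v 5 (1 v 2, 9.3.1 only).
- Assumed: normal data, equal SD, resampling within arm, nominal 95%. Near-normal data are where 8.1.1 keeps the mean.

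**Step 1. Closed-form approximation for equal arms.** A percentile or basic interval behaves roughly like the mean difference ± 1.96 × √(plug-in variance). The plug-in variance divides by n rather than n − 1. In units of the usual standard error the multiplier is therefore 1.96 × √((n − 1)/n). With equal n and equal SD, the standardised difference follows a t distribution on 2n − 2 degrees of freedom.

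- 5 v 5: 1.96 × √0.8 = 1.753; the t value needed on 8 df is 2.306; coverage = P(|t₈| < 1.753) = 88.2%.
- 10 v 10: 1.96 × √0.9 = 1.859; the t value needed on 18 df is 2.101; coverage = P(|t₁₈| < 1.859) = 92.1%.
- 5 v 10 (same approximation, by simulation of the two variances): 89.4%.

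Both the variance and the multiplier are too small. The basic and BCa forms do not repair this.

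**Step 2. Simulation of the bootstrap intervals.** Percentile, basic and BCa coverage uses 1,999 resamples and more than 22,000 data sets per pair (Monte Carlo SE at most 0.06 points). The studentised and Welch columns come from 10,000 data sets.

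| Pair | Percentile | Basic | BCa | Studentised | Welch t |
|---|---|---|---|---|---|
| 5 v 5 | 87.9% | 87.9% | 87.8% | 95.2% | 95.3% |
| 5 v 10 | 88.9% | 88.9% | 88.8% | 94.6% | 94.8% |
| 10 v 10 | 91.9% | 91.9% | 91.8% | 95.2% | 95.3% |

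**Step 3. Null comparisons excluding zero** (100% minus percentile coverage).

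- Dose contrasts, 5 v 10: 100 − 88.9 = 11.1%.
- Sequence contrast, 10 v 10: 100 − 91.9 = 8.1%.
- Treatment 1 v 2, 5 v 5: 100 − 87.9 = 12.1%.

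**Step 4. Departures from the assumptions** (percentile, difference in means).

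- SD ratio of 2: 5 v 10 covers 86% if the arm of 5 varies more and 90% if the arm of 10 does; 10 v 10 covers 91%.
- Mild skew (lognormal, log SD 0.5, 1- to 3-fold difference, raw scale): 88–90% for 5 v 10 and 89–91% for 10 v 10.

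**Step 5. Median branch.** On normal, equal-SD data the percentile interval for a difference in medians covers 96–97% for all three pairs. The shortfall is confined to means.

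**Step 6. Width of the replacement.** Mean widths in SD units, Welch over percentile: 10 v 10, 1.87/1.63 = 1.15; 5 v 10, 2.47/1.89 = 1.31; 5 v 5, 2.93/2.13 = 1.38. Ratios based on median widths are within about two percentage points of these.

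**The case against.** The strongest reply is that the SAP does not choose a bad interval. A studentised bootstrap satisfies the sentence as written and is near nominal on normal data, so the shortfall depends on a choice not yet made. The median option does not under-cover at these sizes. These are secondary comparisons in a 34-person phase 1 trial whose primary objective is safety. All of that stands. It makes this an under-specification whose usual default is poor, not a demonstrated error.

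Four stronger readings are tempting, and the documents do not support them.

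- **That the trial's tests have an 8–12% error rate.** Section 8.1.1 sets a separate p-value rule for tests and does not make exclusion of zero a decision rule. The 12% belongs only to Treatment 1 against 2 for neutralization, and only if magnitude is compared. It does not describe the dose or sequence contrasts.
- **That ICS arms fall to 4 and 8.** Section 9.2 gives "Part A (n=11), visit 4 (1 month (M) post vaccination" and 20 for Part B, but does not say who is missing. Twenty is also the number of Part B vaccinees. Arm sizes of 4 or 8 are conjecture.
- **That vaccine-placebo intervals against 2 participants are the main defect.** Section 8.1.1 says control arms are typically pooled for display, and 9.3.1 allows response rates alone. After Month 1 the neutralization and binding schedules leave only the 2 Part B placebo recipients, but how to present them is a side matter.
- **That requiring the studentised bootstrap is a safe general remedy.** With 80% of both arms at the assay floor (assumed), more than 2.5% of resamples had a zero standard error in 61% of 5 v 10 and 42% of 10 v 10 data sets, which leaves that interval ill-defined. Welch held at about 95–97% in the floored cases. On strongly skewed raw data (log SD 1, 3-fold difference, 10 v 10), Welch and the studentised bootstrap both cover only 88%, against 84% for percentile. Scale therefore has to be settled as well as interval type.

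**Conclusion.** The concern holds as a gap in specification with a measurable consequence. If the intervals for means are percentile, basic or BCa, and readouts are roughly normal with equal SD, nominal 95% intervals cover about 89% for the dose contrasts and 92% for the sequence contrast, and about 88% for Treatment 1 v 2 in neutralization. The SD and distribution are assumed. Unequal SD or mild skew gives 86–91% for the dose and sequence contrasts.

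Which assays are affected depends on whether the mean or the median is used, and 8.1.1 does not say how a severe departure from normality is to be judged. Point estimates, the Dunnett analysis of AUC-MB in 8.1.3, the rank and Kolmogorov-Smirnov options in 8.1.5 and the primary safety objective are not affected. The change should be made, because a better method is available at almost no cost.

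**What to change.** In Section 8.1.1, state a 95% level and replace the unspecified bootstrap interval for means with a Welch t interval. Use the log scale for neutralization and binding titers, which agrees with the natural-log titers in 9.3 and the geometric means in 9.4.

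In Section 9, fix for each assay the analysis scale and whether the mean or the median is compared. ICS percentages and net MFI need an explicit choice, because background-subtracted values can be zero or negative and a log scale is then not directly available. Do not write in the studentised bootstrap as a general fallback.

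The cost is SAP wording only: no new participants, samples or assays. On normal, equal-SD data, Welch intervals are about 15% wider than percentile intervals for 10 v 10, 30% for 5 v 10 and 37% for 5 v 5. That extra width is what brings coverage to about 95%.
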